Official Title: Effects of Toe-out Gait Modification on Clinical and Biomechanical Measures in People with Knee Osteoarthritis

- NCT Number: NCT02019108
- **Document Date:** November 25, 2013

Methods

Participants

Community-dwelling individuals were recruited via an existing laboratory database as well as advertisements in print media. Inclusion criteria were: (i) definitive medial tibiofemoral osteophytes on x-ray; (ii) joint space narrowing greater in the medial tibiofemoral compartment compared to the lateral compartment; (iii) history of knee pain longer than six months; and (iv) average knee pain of at least 3 out of 10 over the one month period prior to initial screening. Exclusion criteria were: (i) knee surgery or intra-articular pain relief injection within six months; (ii) current or past (within six months) oral corticosteroid use; (iii) history of knee joint replacement or tibial osteotomy; (iv) any other condition affecting lower limb function; (v) participation in a new structured exercise program within the past three months, or planning to commence exercise or other treatment for knee OA in the next four months; and, (vi) an inability to travel to the university to attend testing and training sessions. The study was approved by the Institution's Clinical Research Ethics Board and all participants provided written informed consent.

Sample size was determined based on randomization with stratification, and covarying for baseline values in the statistical analysis. Using effect size estimates of 0.8 for WOMAC pain and 1.0 for KAM impulse, based on pilot data using a similar design, it was determined that participants in each group was required to attain 90% power to detect significant differences in pain and KAM outcomes between groups with an alpha of 0.05. Using a conservative estimate of 10% attrition, the aim was to recruit 73 participants for this study.

Study Design

This was a parallel group, assessor-blinded, randomized controlled trial. Interested participants were initially screened for inclusion and exclusion criteria over the telephone and eligible individuals then underwent a physical screen. Screening was overseen by a researcher not involved in data collection or analysis.

This physical screen was conducted to confirm the presence of knee pain, and to perform a preliminary walking assessment to assess self-selected foot progression angle. Participants performed three trials of self-selected, over ground walking while three reflective skin markers tracked the movement of the sacrum, the second toe, and posterior calcaneus of the study limb (defined as the self-declared osteoarthritic limb in those with unilateral symptoms, or the most painful limb in the case of bilateral symptoms). The mean foot progression angle across the three trials was calculated. As the goal of the toe-out modification program was to increase the self-selected, baseline foot progression angle by 15° in the toe-out direction, 15° of toe-out at the physical screening was selected as the threshold. This was done due to (i) the difficulty in achieving toe-out angles of 30° by people with knee OA, and (ii) the fact that those who already exhibit large amounts of toe-out would likely not be candidates for toe-out gait modification in the clinical setting.

Those who passed physical screening were referred for radiographic evaluation. Standing, semiflexed, postero-anterior radiographs were obtained and graded for disease severity using the Kellgren and Lawrence (KL) OA classification system.

Individuals who met the radiographic criteria listed above were invited to the laboratory for a baseline (Week 0) testing session where self-report questionnaire, objective physical function, and biomechanical data were collected. Following completion of baseline testing, the randomization procedure was conducted by a study biostatistician who was not involved in any aspect of data collection or training. Randomization was initiated by the study research coordinator, who provided the biostatistician with each participant's study ID, sex, and KL grade. The biostatistician then responded via email with the group allocation, and maintained the randomization parameters and list offsite. Group allocations were determined prior to study commencement, and randomization was stratified by sex (male, female) and disease severity (mild or moderate grouped together, severe).

Participants returned to the university the following week (Week 1) to begin their training program, and were informed of their group allocation at this time. Each home-based program lasted four months and was supplemented with eight training sessions with the study trainer at Weeks 1, 2, 4, 6, 8, 10, 12 and 15 of the intervention, with typical sessions lasting 20 minutes in Week 1 and increasing to 40 minutes by Week 15. All training sessions, regardless of group allocation, were conducted by the same trainer in the same rehabilitation gymnasium. The first training session for each participant was always a one-on-one session with the trainer, with subsequent sessions conducted in groups of one to three individuals; in cases of group sessions, only individuals from the same group allocation were present in the gymnasium to prevent cross-contamination of groups.

Follow-up testing occurred four months after baseline testing, with a final retention testing session conducted one month later. The same outcome measures, completed in the same testing order, and by the same blinded assessor, were collected at each testing session. No training or instructions of any kind were provided between these final two testing sessions.

Interventions

For both groups, the intent was to increase the weekly amount of walking out in the community by 40% over and above that exhibited prior to enrollment. Initial values were assessed via discussion with participants at the first training session, and prescribed weekly increases were determined individually at each training session in consultation with the trainer.

Toe-out (TO) gait modification program

Participants randomized to the TO program were trained to perform walking with 15° more toeout than the self-selected amount measured at the baseline testing session. Our previous pilot study showed modest improvements of 6.7° in self-selected toe-out angle following 10-weeks of toe-out gait retraining intending to increase toe-out by 10°, that resulted in marginally statistically significant improvements in late stance KAM (p=0.04) and self-reported pain (p=0.02), and non-significant decreases in KAM impulse (p=0.20). Thus, a larger toe-out increase was selected for this study.

Toe-out modification during the training sessions was facilitated with mirror-guided biofeedback of performance. Participants placed their study foot on a protractor device at the target toe-out angle for that session, and verbally instructed the therapist in the placement of a piece of green tape on the mirror to best cover the reflection of the foot in this target position. The tape remained on the mirror during the training session to guide foot placement during treadmill walking. To promote motor learning, a faded feedback paradigm was used with removal of real-time biofeedback commencing at session 4 (mean percentage of walking time with feedback: Week 6 = 90%; Week 8 = 75%; Week 10 = 60%; Week 12 = 45%; Week 15 = 35%). Self-reported difficulty in achieving the target angle was recorded at each training session using an 11-point numerical rating scale (NRS) with terminal descriptors of 0 = "no difficulty" and 10 = "unable to perform"). Participants were instructed to maintain the increased toe-out angle outside the training sessions whilst walking in the community.

Progressive walking (PW) program

Participants randomized to the PW program underwent all training procedures as those in the TO group, with the exception of receiving no training or instruction related to toe-out walking. This included walking on the treadmill in front of a mirror during training sessions, but without foot placement guide tape as per the TO training protocol.

Outcome measures

Pain and physical function

At each testing session, participants completed the Western Ontario and McMaster Universities Arthritis Index (WOMAC) Likert version₂₂. Average knee pain over the previous week was also assessed using an 11-point NRS with terminal descriptors of 0 = "no pain" and 10 = "worst pain imaginable". Overall perceived change at follow-up compared to baseline was assessed using a 15-point Likert scale (-7 = "a very great deal worse" 0 = "about the same", +7 = "a very great deal better"). Finally, participants completed the timed stair climb test where they were instructed to ascend 12 stairs "as quickly as possible", and the fastest time from the two attempts was recorded.

Gait biomechanics

Gait data were recorded for barefoot, over ground walking trials at a self-selected speed. Twentytwo retro-reflective markers were affixed to the participant according to a modified Helen Hayes marker set, and their movements were captured using twelve high-speed digital cameras (Motion Analysis Corp., Santa Rosa, CA) sampling at 100 Hz. An initial standing static trial was collected using additional markers placed over the medial malleoli and femoral epicondyles to determine segment orientations and joint centres of rotation. Kinematic data from the cameras were synchronized with two force platforms (OR6-6, Advanced Mechanical Technologies Inc.) visually concealed in the floor of a 10m walkway and sampling data at 2000 Hz. Participants were provided no instructions pertaining to walking mechanics during any of the gait assessments.

Inverse dynamics techniques and commercially available software (Orthotrak, Motion Analysis Corp.) were used to calculate gait variables including: KAM (early stance peak, late stance peak, impulse), peak external knee flexion moment (KFM) during stance, and mean foot progression angle during foot-flat (positive values = toe-in orientation, negative values = toe-out orientation). The mean value from five walking trials was calculated for each biomechanical variable.

Adherence, concurrent treatments, and adverse events during interventions

Adherence to both training programs was assessed as the total number of supervised walking sessions attended for each participant. Compliance with the prescribed walking increases was obtained from log book data completed by participants detailing their daily amount of walking for the duration of the study, and weekly totals (in hours) were calculated. Additionally, an 11-point NRS (0 = "not confident at all", 10 = "very confident") in the log book was used to assess self-reported confidence in the ability of those in the TO group to maintain the increased toe-out angle whilst walking in the community. Finally, concurrent treatments and adverse events reported during the intervention were assessed using open-ended questions in the log book maintained by the participants. For the purposes of analysis, adverse events were defined as those lasting longer than two weeks in duration, or requiring additional treatment.

Statistical analysis

The primary outcomes were WOMAC pain, KAM impulse, and foot progression angle, and the primary endpoint was the follow-up assessment. All other biomechanical and clinical outcomes were considered secondary in nature. Between-group comparisons were the primary analyses, with within-group comparisons used for informational purposes. Analysis of covariance (ANCOVA) models were fit predicting each outcome variable evaluated at both time points (follow-up and retention), with group as predictor, and while controlling for baseline values. For biomechanical outcomes (knee adduction and flexion moments, as well as foot progression angle), additional models were computed while additionally controlling for concurrent gait speed at the associated time point (follow-up or retention). For baseline data, crude means were computed. Adjusted least squares means (LS means) with standard errors and 95% confidence intervals were computed for each group at both follow-up and retention. Adjusted LS means were computed in similar models for within-group (delta) scores. Finally, model-adjusted group effects were computed, along with p-values and 95% confidence intervals, for all outcomes.

All data were analyzed using an intention-to-treat analysis, and the primary analyses assumed that data were missing completely at random (MCAR). In sensitivity analyses, multiple imputation was performed as per the methods described by van Buuren. Results and conclusions were compared to the MCAR analysis, and any differences noted. All statistical analyses were conducted by a biostatistician blinded to group allocation and who was not involved in any other aspect of the study. Analyses were performed using SAS v9.4 (SAS Institute, Cary, North Carolina).

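### Does the pilot's p=0.20 for KAM impulse undermine the planning effect of 1.0 and the stated 90% power?

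*Combined protocol and SAP*

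**What the plan says.** In the combined protocol and SAP, the sample-size paragraph under Participants sets the planning inputs "Using effect size estimates of 0.8 for WOMAC pain and 1.0 for KAM impulse, based on pilot data using a similar design". It says the resulting group size is enough "to attain 90% power to detect significant differences in pain and KAM outcomes between groups with an alpha of 0.05", and after 10% attrition it aims for 73 participants. The number per group is missing from the text as extracted; that gap is not held against the plan.

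The Toe-out (TO) gait modification program section describes a previous pilot. It found "modest improvements of 6.7° in self-selected toe-out angle following 10-weeks of toe-out gait retraining intending to increase toe-out by 10" degrees. Its results included a late-stance KAM improvement (p=0.04) and "self-reported pain (p=0.02), and non-significant decreases in KAM impulse (p=0.20"). The section concludes: "Thus, a larger toe-out increase was selected for this study". In this trial participants are "trained to perform walking with 15° more toeout than the self-selected amount measured at the baseline testing session", and under Study Design, "Each home-based program lasted four months".

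Under Statistical analysis, "The primary outcomes were WOMAC pain, KAM impulse, and foot progression angle". The same section provides for model-adjusted group effects with 95% confidence intervals for every outcome.

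**The concern.** The planning effects put KAM impulse above pain (1.0 against 0.8) and attribute both to pilot data. The one pilot on the page points the other way: pain was significant and KAM impulse was not. A reader who joins the two sections will suspect that 1.0 is not a pilot estimate at all, or that it silently includes an allowance for the larger toe-out target.

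KAM impulse is one of three primary outcomes, so this would matter. If the true effect were near 0.4, the trial would have roughly one chance in three of detecting it. A reader who took 90% at face value could then mistake a non-significant KAM impulse result for evidence of no effect.

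**Working it through.** **Inputs.** From Participants: effects 0.8 and 1.0, power 90%, alpha 0.05, attrition 10%, target 73. From the toe-out program section: pilot p-values 0.02 (pain) and 0.20 (KAM impulse), pilot target 10°, pilot change 6.7°, trial target 15°. Assumed, because not stated: two-sided testing, 1:1 allocation, and 33/32 completers (73 × 0.9 = 65.7).

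**1. The plan's own figure.** For pain at 0.8, n per group = 2(1.960 + 1.282)² / 0.8² = 32.8, so 33. Then 66 / 0.9 = 73.3, which matches 73. For 1.0 the same formula gives 2(1.960 + 1.282)² / 1.0² = 21.0, or 22 when rounded up. Pain therefore sets the sample size; the 1.0 does not enter it.

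**2. Power at the stated effects.** Noncentral t with 33/32 gives 88.8% at 0.8 (89.3% with 33/33; 90.1% by the normal approximation) and 97.8% at 1.0. If 1.0 is accepted, the 90% statement is true for KAM impulse with room to spare.

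**3. What the pilot p-values imply, if that pilot is the source.** With the same participants and the same kind of test, the ratio of test statistics equals the ratio of standardised effects.
- Normal: 1.282 / 2.326 = 0.551.
- t with 8 df: 1.397 / 2.896 = 0.482.

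The planning ratio is 1.0 / 0.8 = 1.25. Holding pain at 0.8, KAM impulse would be 0.8 × 0.482 = 0.39 to 0.8 × 0.551 = 0.44.

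**4. Allowing for the larger target.** The scenarios assume that effects are on the baseline-adjusted scale and scale linearly with degrees of toe-out achieved.

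| Toe-out change achieved | Multiplier | KAM impulse effect | Power |
|---|---|---|---|
| 6.7°, as in the pilot | 1 | 0.39 to 0.44 | 34% to 42% |
| 67% of 15° = 10.05° | 10.05 / 6.7 = 1.5 | 0.59 to 0.66 | 64% to 75% |
| 15°, full target | 15 / 6.7 = 2.24 | 0.87 to 0.99 | 93% to 97% |
| Stated planning value | n/a | 1.0 | 97.8% |

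An effect of exactly 1.0 would need 6.7 / 0.44 = 15.2° to 6.7 / 0.39 = 17.2°, slightly beyond the target.

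**5. Sensitivity to the scale.** If the pilot-derived effects are on the raw scale and the baseline correlation is 0.7 (an assumption), each effect is divided by √(1 − 0.49) = 0.714. The first row becomes 58% to 69% and the second 90% to 96%.

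**6. What the design can detect, whichever pilot was used.** With 33/32, the detectable effect is 0.82 baseline-adjusted SD at 90% power and 0.71 at 80%. The 95% confidence interval half-width is t(63) × √(1/33 + 1/32) = 0.50 adjusted SD.

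**The case for a change.** The strongest case for acting is that the gap between 0.5 and 1.25 is too wide for rounding: allowing for rounded p-values moves the normal ratio only to 0.52 to 0.58. Had KAM impulse really been 1.25 times pain in that pilot, its p-value would have been about 0.004 to 0.007, not 0.20. If 1.0 includes scaling for the larger target, the plan does not say so, and nothing explains why pain stayed at 0.8. Under linear scaling, 90% power needs 6.7 × 0.817 / 0.44 = 12.4° to 6.7 × 0.817 / 0.39 = 14.0°, or 83% to 94% of the target, where the pilot reached 67% of its own. A sentence or two would settle it.

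That arithmetic stands, but its premise is not in the document. Neither section refers to the other, and the toe-out section uses its pilot only to justify the 15° target. A citation naming a different pilot may have been lost in extraction, since the text has kept a stray reference number elsewhere. The ratio also needs a comparable test for both outcomes, and it needs the pilot's unnamed pain measure to be WOMAC pain. This trial itself uses two pain scales. If the pilot was pre-post and the effects were expressed in raw SD units, the ratio could lie anywhere from 0.21 to 1.46. Values near 1.25 do require pain to be much more highly correlated over time than KAM impulse, and on the baseline-adjusted scale the ratio stays between 0.46 and 0.67.

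What remains is that the origin of 1.0 is not written down.

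**Conclusion.** No change is needed. The sample size rests on pain at 0.8 and reproduces. The KAM impulse power statement names its assumed effect and holds at that effect (about 98%). The lowest figures, 34% to 42%, require that the described pilot is the source, that its tests and pain measure are comparable, that effects are on the adjusted scale, and that participants achieve no more than 6.7° despite a target raised for exactly that reason. At the full 15° the same reasoning gives 93% to 97%. The stated power may be optimistic, but the document does not show that it is wrong.

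The risk of misreading a null result is also largely covered. The planned 95% confidence intervals will show which effects remain open: with a half-width of about 0.50 adjusted SD, an estimate of zero would plainly leave effects of 0.4 to 0.5 possible. Stating where 1.0 came from, or quoting the detectable effect of 0.82 adjusted SD at 90% power, would help a reader, but it would alter neither the sample size, the design, the analysis nor any result.

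### The walking level that anchors the 40% increase in both arms is taken at the Week 1 session where allocation is disclosed, not before randomisation, so knowledge of allocation could influence it

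*Combined protocol and SAP*

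**What the plan says.** The Interventions section gives both arms the same walking aim: "the intent was to increase the weekly amount of walking out in the community by 40% over and above that exhibited prior to enrollment". It then says how the starting level is found: "Initial values were assessed via discussion with participants at the first training session". The rest of that sentence has the increases set person by person at every training session, with the trainer's input.

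The Study Design section fixes the timing. Week 0 testing covers questionnaires, function tests and gait data, and randomisation follows it. Participants come back in Week 1 to start training and "were informed of their group allocation at this time". On who is present: "The first training session for each participant was always a one-on-one session with the trainer". On who delivers the programs: "All training sessions, regardless of group allocation, were conducted by the same trainer in the same rehabilitation gymnasium".

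Under the progressive walking program, the comparator is described as matching the toe-out program in everything except toe-out training and instruction.

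The adherence section says: "Compliance with the prescribed walking increases was obtained from log book data completed by participants". The logs record daily walking and are totalled as hours per week.

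The Statistical analysis section specifies ANCOVA with group and the baseline value of the outcome, and gait speed in additional models for biomechanical outcomes. It has no term for walking volume and no comparison of walking hours between arms.

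**The concern.** The comparator isolates toe-out training only if the two arms are asked for the same relative increase in walking. That increase is a multiple of a stated starting level. The starting level therefore helps determine the treatment each person is prescribed; it is more than a descriptive adherence item.

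The level is obtained after randomisation, at the visit where the group is revealed, with a trainer who has to know the arm to run the session. The blinding of the outcome assessor and of the analyst does not reach this step. The plan describes no script, recall instrument or allocation-blind procedure for it.

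If the level were shaded differently in the two arms, they would be prescribed different real increases under the same nominal 40%. To the extent that walking volume affects knee pain, a difference in WOMAC pain could then not be credited to toe-out alone. WOMAC pain is the primary outcome most exposed; KAM impulse and foot progression angle are less so.

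**Working it through.** **Sequence of events, from Study Design and Interventions**

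| Step | When | Walking level recorded? |
|---|---|---|
| Baseline testing | Week 0 | Not listed |
| Randomisation | After baseline testing | No |
| Allocation disclosed to participant | Week 1 | – |
| First training session, one-on-one | Week 1 | Yes, by discussion |

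The other individual anchor in the plan is handled differently. The toe-out target is set from the angle measured at the baseline testing session, which precedes randomisation. Only the walking anchor is left until after it.

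**Inputs.** The 40% increase comes from Interventions. The size of any error in the stated level is not in the documents; 5% to 20% is an assumed range, in either direction.

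**Formula.** Let T be true pre-enrolment weekly walking and S = T × (1 + b) the stated level. If the prescription is 1.40 × S:

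- true target as a multiple of T = 1.40 × (1 + b)
- true increase = 1.40 × (1 + b) − 1
- total walking relative to an arm without error = 1 + b

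With b = 0 this returns the plan's own figure: 1.40 × 1 − 1 = 40%.

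| b in one arm | Target, × true baseline | True increase | Total walking relative to other arm |
|---|---|---|---|
| −20% | 1.12 | 12% | 0.80 |
| −10% | 1.26 | 26% | 0.90 |
| −5% | 1.33 | 33% | 0.95 |
| 0 | 1.40 | 40% | 1.00 |
| +5% | 1.47 | 47% | 1.05 |
| +10% | 1.54 | 54% | 1.10 |
| +20% | 1.68 | 68% | 1.20 |

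**Partial carry-through.** Because increases are reset individually at each session, only a fraction c of the error may reach the prescription. The target is then 1.40 × (1 + c × b). With b = −10% and c = 0.5 (assumed), 1.40 × 0.95 = 1.33, or 5% less total walking.

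**Error common to both arms.** If both arms err by the same b, the ratio is (1 + b)/(1 + b) = 1 and the between-arm contrast is unaffected. Only a differential error matters.

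**What the log book would show.** Take b = −10% with full adherence. The person walks 1.40 × 0.90 × T = 1.26 T, and the prescription is also 1.26 T. Compliance is 1.26/1.26 = 100%, so nothing appears amiss. Randomisation makes mean T equal across arms in expectation, so average logged hours would stand at 1.26/1.40 = 0.90 of the other arm's. Comparing hours directly can therefore pick up what compliance against target cannot.

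The recruitment target of 73 does not enter any of this.

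**The case against.** The strongest reply is that nothing points to a differential error. Both arms receive an active walking program with the same aim, from one trainer in one gymnasium. Recall error shared by the arms cancels. The change of method, from discussion at the start to log book afterwards, applies to both arms alike and does not by itself bias the comparison. One can imagine a more cautious starting figure for people who must also hold a new foot angle on every community walk, but that is conjecture. All of this stands, and it keeps the point to a possibility.

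The 40% is stated as an intent, with increases set individually over eight sessions. The tabulated values are therefore the full-carry-through case, not an estimate. That also stands.

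Two steps are inferred. The text does not say whether the discussion came before or after disclosure within Week 1, nor in so many words that the trainer obtained the value. The inference is reasonable: the session is one-on-one, its trainer must know the arm, and nothing places the discussion first.

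A reader might infer that the log book could not expose a difference in walking between arms. The documents do not support that: weekly hours are calculated from the same record in both arms. The check is only partial, because the logs are completed by unblinded participants, no between-arm comparison is specified, and no pre-enrolment value in log-book form is described. The logs are said to run throughout the study, which might be read to include Week 0, but the section heading confines them to the intervention period.

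**Conclusion.** The point holds as a minor, inexpensive improvement to the design. The plan takes an anchor shared by both arms at the visit where allocation is disclosed, although an earlier visit before randomisation was available and was used for the toe-out anchor. Knowledge of allocation could influence the walking anchor and hence the walking prescribed.

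Its possible size is illustrative. With a one-arm error carried fully into the prescription, a 10% understatement lowers the true target from 1.40 to 1.26 times baseline and a 20% understatement lowers it to 1.12. In total weekly walking these are reductions of 10% and 20%, which is the fairer scale than the fall in the increment alone. Both the error range and the full carry-through are assumptions.

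A reader might go further and infer that the arms did receive different amounts of walking, or that the WOMAC pain comparison is biased. The documents support neither. They report no walking volumes by arm, and they give no relation between walking volume and pain from which an effect on the primary result could be derived.

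**What to change.** 1. At the Week 0 session, before randomisation, ask each participant for usual weekly walking hours before enrolment, in the same units as the log book.
2. Use that value as the starting level for the increase in both arms, in place of the Week 1 discussion.
3. Specify in the Statistical analysis section a by-arm report of logged weekly hours and of change from the Week 0 value.

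The question should ask about usual walking before enrolment. Having participants log the week between Week 0 and Week 1 would not serve, because that week falls after enrolment and keeping a log may itself change walking.

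The 40% aim, the individual setting of increases and the sample size stay as they are. The change protects the anchor only. The trainer would still set later increases knowing the arm, which is why the by-arm report of hours is needed as well. If the starting level has already been collected as described, logged hours by arm can still be reported from the existing records.

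The cost is one extra questionnaire item at a visit that already takes place, and one descriptive table.

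### Adverse event and concurrent treatment capture is described only for the intervention, although the arms are compared again at a retention test one month after follow-up

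*Combined protocol and SAP*

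**What the plan says.** The section headed "Adherence, concurrent treatments, and adverse events during interventions" sets the window twice. Its heading limits the scope to the interventions, and its text says that "concurrent treatments and adverse events reported during the intervention were assessed using open-ended questions in the log book maintained by the participants". For analysis, "adverse events were defined as those lasting longer than two weeks in duration, or requiring additional treatment". An event therefore qualifies by either of two routes: duration or treatment.

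Study Design gives the calendar: "Each home-based program lasted four months and was supplemented with eight training sessions". Follow-up testing is four months after baseline, "with a final retention testing session conducted one month later". For that last month the plan adds: "No training or instructions of any kind were provided between these final two testing sessions".

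Two other statements bear on the point. The toe-out program section tells participants to keep the larger angle when walking in the community and gives no end date. The log book is described, for walking, as "detailing their daily amount of walking for the duration of the study". Whether that includes the retention month is not said.

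Statistical analysis makes follow-up the primary endpoint. It fits a baseline-adjusted between-group model for every outcome at follow-up and at retention.

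**The concern.** Efficacy is compared out to five months, while harm capture is described only to about four. A report that follows the plan could describe benefit at retention beside safety data that stop a month earlier, and the reader would have no record of individual events in between.

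The analysis definition shortens the useful window further. If recording stops when the intervention ends, an untreated event that began in the final two weeks has not yet lasted long enough to qualify. If treatment is first sought after the intervention, the second route is closed as well. The plan has no rule for events open at that point.

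Concurrent treatments fall under the same restriction, and this touches efficacy too. WOMAC pain is compared between arms at retention, but a treatment started in the retention month is not described as recorded. A difference, or its absence, at that visit would be harder to interpret.

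**Working it through.** The plan gives no figure on this point, so there is none to reproduce. The check has two parts: reading the windows side by side, and measuring the gap.

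**Windows**
- Adverse events and concurrent treatments: the intervention only (section heading and text).
- Outcome measures: baseline, follow-up and retention (Study Design; Statistical analysis).
- Walking log: the duration of the study, end not defined (adherence section).
- Events open at the end of the intervention: no rule anywhere.

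**Inputs**
- Program length of four months, follow-up at four months from baseline, retention one month later, first training session at Week 1 (all from Study Design).
- Duration criterion of more than two weeks (adherence section).
- Assumption: one month = 52.18/12 = 4.35 weeks, so four months = 17.39 weeks and five months = 21.74 weeks.

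**Time with no described capture of new events**
- Reading A, capture ends four months after baseline: 21.74 − 17.39 = 4.35 weeks. Share of baseline-to-retention time: 4.35/21.74 = 20%.
- Reading B, the four-month program starts at Week 1: it ends at 1 + 17.39 = 18.39 weeks, leaving 21.74 − 18.39 = 3.35 weeks. Share of the time from Week 1 to retention: 3.35/(21.74 − 1) = 3.35/20.74 = 16%.
- The text does not settle which reading applies, so the result is a range of 16% to 20%.

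**Late untreated events within the intervention**
- The last two weeks are 2/17.39 = 11.5% of the intervention, or 2/16 = 12.5% if four months is taken as 16 weeks. This applies only to events that do not require treatment during the intervention.

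**Time closed to an untreated event that qualifies on duration**
- As written, Reading A: (4.35 + 2)/21.74 = 6.35/21.74 = 29%. Reading B: (3.35 + 2)/20.74 = 5.35/20.74 = 26%.
- With collection extended to the retention test, the two-week blind spot moves to the end of the longer window: 2/21.74 = 9% (Reading A) or 2/20.74 = 10% (Reading B).
- Time recovered by the extension: 6.35 − 2 = 4.35 weeks, or 5.35 − 2 = 3.35 weeks. These are the same 20% and 16% as above.

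These are shares of time, not of events. The plan gives no event rate and no onset pattern, so they cannot be turned into a count.

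**The case against.** Much can be said for the plan. Follow-up is the primary endpoint, and harm capture through the intervention broadly matches it. The same outcome measures are taken at retention by a blinded assessor, so an average worsening of knee pain or function in one arm would show there. The log book may have run into the retention month with its adverse event questions still in it. All of this stands. None of it supplies a stated collection of individual events, non-knee complaints or new treatments in that month, and the adverse event sentence keeps its own, narrower window.

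A reader might also draw stronger conclusions that the documents do not support:
- **That every event must last more than two weeks.** The definition also admits events that require treatment. A late event treated during the intervention counts at once.
- **That toe-out walking is expected to continue to retention.** The instruction to keep the angle has no end date, and foot progression angle is measured again at retention, so continued exposure is a fair inference. But participants received no instruction in that month either to continue or to stop. A claim that harm is hidden in the toe-out arm in particular depends on this inference.
- **That about 29% of duration-qualifying events are lost.** This needs a constant onset rate, for which the plan offers no support. It also exceeds what a longer window can recover, because a two-week blind spot remains before the retention test.
- **That the retention month is the only unsupervised time.** The programs are home-based and the last session is at Week 15, so on Reading A about 17.39 − 15 = 2.4 weeks before follow-up also have no trainer session.

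**Conclusion.** The point holds in a limited form. As written, the window for adverse events and concurrent treatments closes before the last between-group comparison, and events open at closure have no rule. New events in some 3.35 to 4.35 weeks (16% to 20% of follow-up) fall outside the described window. Untreated events starting in the last two weeks of the intervention cannot be seen to qualify on duration.

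The range rests on the month-to-week conversion and on where the four-month program is counted from. It also takes the adverse event sentence at its word over the looser description of the walking log. That events actually went unrecorded, or that the loss falls more on the toe-out arm, is possible but not shown.

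No primary analysis is affected. This is a change that should be made because it improves safety ascertainment and the reading of retention outcomes at little cost.

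**What to change.** In the adverse event sentence of the adherence section, replace the restriction to the intervention with a window running from the first training session to the retention test, for both adverse events and concurrent treatments. Bring the section heading into line. State that the log book, with these questions, continues through the retention month.

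At the retention visit, for every event open at follow-up or starting afterwards, record an end date or that it is ongoing, and any treatment received. Apply the existing definition to that completed record. List separately the untreated events that began within the two weeks before the retention test and are still ongoing, since their duration cannot yet be judged. Report events and concurrent treatments by arm, for the intervention and the retention month separately.

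The log book and the visit already exist. The cost is protocol wording, about four more weeks of diary burden for participants, and possibly a higher reported event count.
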